3.3 Exploratory objectives and endpoints

Exploratory objectives	Exploratory endpoints
To evaluate the clinical efficacy of mavrilimumab compared to the control arm by clinical severity (i.e. mild vs	To evaluate the primary and secondary endpoints in different subgroups of patients:
moderate subgroup)	- mild respiratory failure: $PaO_2/FiO_2 \le 300$ and > 200 mmHg;
	- moderate respiratory failure: $PaO_2/FiO_2 \le 200$ and > 100 mmHg
To measure the time course of the effects of mavrilimumab on biomarkers associated with but not restricted to those possibly linked to inflammation and disease	Changes in exploratory biomarkers: - Inflammatory biomarkers (i.e. IL-6, IL-1RA, TNF-alpha, CBC and differential) - Levels of antibodies to SARS-CoV-2 / SARS-Cov-2 positivity by PCR
	Levels of anti-drug antibiodies (ADA)

4. Study design

This is a multicenter, randomized, double-blind, placebo-controlled study to assess the efficacy and safety of mavrilimumab plus standard-of-care (SOC) compared with placebo plus SOC in adult patients with COVID-19-induced pneumonia and systemic hyperinflammation. The study aims to randomize approximately 50 patients throughout the participating centers. Enrollment will stop as soon as the target number of randomized subjects is reached. Patients who meet the inclusion/exclusion criteria will be randomized in a 1:1 ratio to either mavrilimumab + SOC or placebo + SOC and can be dosed immediately after ensuring that the patient has met all eligibility criteria. Randomization will be balanced according to the following strata (in descending order of priority):

- Age (<50; 50-69; \ge 70 yo);
- Mild respiratory insufficiency (as defined by a $PaO_2/FiO_2 \ge 200$ and < 300 mmHg) vs. moderate respiratory insufficiency (as defined by a $PaO_2/FiO_2 \ge 100$ and < 200 mmHg) at randomization.

Patients in the mavrilimumab arm will be dosed on Day 1 with a dose of 6 mg/kg (using a solution with a final concentration of mavrilimumab of 50 mg/mL) infused IV over approximately 1 hour. Patients in the placebo arm will be treated with an equal amount of placebo infused IV over approximately 1 hour.

An informed consent will be obtained from patients before assessments solely required for the study are performed. Thereafter, eligibility criteria will be reviewed by study personnel. All patients with signed informed consent must be registered in an *ad hoc* prepared Interactive Response Technology (IRT) system.

Eligible patients will have biomarker sampling according to the Assessment and Procedures Schedule (see below). Additional safety assessments will be performed approximately as described in the Assessment and Procedures Schedule. Additional follow-up visits will occur on Days 7, 14, 28, 56 and 84 either by phone if previously discharged or in the hospital if still hospitalized. If a patient is hospitalized for longer than Day 28, all invasive protocol assessments will be discontinued except at week 8 and 12, if still hospitalized. If the patient has been discharged, then patients should be phoned for follow-up and data collected as in the Assessment and Procedures Schedule. In addition, unscheduled visits are permitted at or after discharge, as needed.

Deaths and SAEs will be monitored in real time with routine pharmacovigilance and by an external, independent DSMB in order to detect any unexpected safety signal. The DSMB will function independently of all other individuals associated with the conduct of this clinical trial. Patients who do not meet the criteria for participation in this study (screen failures) may not be re-screened.

4.1 Rationale for study design

This randomized, double-blind, placebo-controlled design supports the assessment of efficacy as well as safety of mavrilimumab plus standard-of-care therapy for patients with COVID-19-induced pneumonia and hyperinflammation.

Currently, no approved treatment for COVID-19 is available. A placebo-controlled study should mitigate the potential biases associated with the clinical setting, the variability of the disease course, and the endpoints related to the study objectives and allow for an objective assessment of mavrilimumab value in this indication. Mavrilimumab and placebo will be blinded by an unblinded pharmacist (or other designated staff member) at each participating Institution.

4.2 Rationale for mavrilimumab dose and administration route

In a Phase 1 single-ascending-dose (SAD) study the pharmacokinetics (PK) of mavrilimumab were tested at doses of 0.01-10 mg/kg in patients with mild-to-moderate RA. Mavrilimumab was well tolerated in a single IV injection up to 10 mg/kg in subjects with mild to moderate RA at all dose levels. (Burmester 2011). Pharmacokinetic and pharmacodynamic simulations from studies in subjects with RA coupled with the PK data from the Phase 1 study, indicate that a single dose of ≥ 3 mg/kg will provide EC90 (the concentration that leads to 90% maximal response) for the RA endpoint ACR50 (American College of Rheumatology 50% response criteria; data on file) for up to 22 days. Therefore, at doses ≥ 3 mg/kg, the pharmacologic profiles indicated sustained peripheral inhibition of the GM-CSF-R α signaling axis for at least three weeks.

In preclinical studies, the potential systemic effects of mavrilimumab (CAM-3001) have been investigated in a 4-week and an 11-week repeat dose cynomolgus monkey study. There were no effects attributable to administration of CAM-3001 (mavrilimumab) in doses up to 100 mg/kg/week for 4 weeks in a study conducted in accordance with Good Laboratory Practice (GLP). In an 11-week exploratory (non-GLP) study there were no effects attributable to IV administration of CAM-3001 (mavrilimumab) following 10 mg/kg/week, and the no observed adverse event level (NOAEL) was 100 mg/kg/week. An immunocytochemistry screen to test in vitro binding of mavrilimumab to a panel of normal human tissues revealed no non-specific or unanticipated binding of the antibody.

Reference for further details on safety studies in animals and humans is made to the Investigator's brochure.

However, with regard to mitigation of the aberrant immune response in the setting of COVID-19, it is unclear whether blockade of GM-CSF in the lung is required in addition to abolition of signaling in the periphery. Studies with the mavrilimumab surrogate anti-mouse GM-CSF-Ra antagonistic antibody, CAM-3003, were performed to interrogate the pulmonary vs peripheral pharmacodynamics of ascending single and repeat doses. Single doses of 3-30 mg/kg delivered intraperitoneally showed no pharmacodynamic effects in the lungs (as assessed by bronchoalveolar lavage (BAL) fluid assay), despite the 3 mg/kg dose demonstrating complete receptor occupancy (RO) in the periphery. Pharmacodynamic effects in the lungs, measured by IL-6 induction from BAL cells (72% ± 11% inhibition), were seen only following repeat daily doses of 30mg/kg. In contrast, daily administration of 3 mg/kg did not affect IL-6 induction of BAL cells. This indicates repeated, very high doses (≥10x required to completely block the signaling axis in the periphery) are required for the anti-GM-CSF-Rα antibody to have an inhibitory effect on alveolar macrophages (Campbell 2016). Campbell et al also indicate that, interestingly, significant pharmacodynamic effects of the antibody on the lung cells could be observed after 5 daily doses of 30mg/kg CAM-3003 (53%±23% inhibition). The authors also indicate that PK studies using BAL measurements to quantify portioning in the lung lumen underestimate the portioning due to dilution with the lavage fluid.

Of further note, these studies were done in mice without underlying lung pathology, and the translatability of these studies in normal mice to humans with COVID-19 pneumonia is unclear. Nevertheless, these data suggest that a dose higher than that needed to achieve 100% RO in circulation may be required in order to achieve therapeutic concentrations in the lung.

In current COVID-19 patients it is likely that the inflammatory process afflicting the lung of severe pneumonia patients with hyper-inflammation may lead to a higher ratio of penetration than the one observed in animal studies, thus allowing for potentially direct inhibitory effects on macrophages which have already migrated in the lungs. Taken together, a dose of up to $10 \, \text{mg/kg}$ IV (the highest tested in humans), may be required to confer significant pharmacodynamic effects in the lung to inhibit cytokine storm and reduce further lung damage. Supported by the safety data provided by the Phase 1 study, it would be reasonable to administer a single dose of mavrilimumab at levels up to $10 \, \text{mg/kg}$ in an attempt to provide desired pharmacodynamics in COVID-19 patients, where direct inhibition of GM-CSF in the lung may be a requirement.

Hypothetically, a dose of 3 mg/kg may be sufficient and reasonable to be tested, but only if the higher proposed dosages in the study, i.e. 6 mg/kg is found not to be safe (very close safety monitoring is proposed) for the target population or if efficacy, if observed, is not apparently dose-dependent. The IV route of administration is supported by Phase 1 (Burmester 2011) safety of SAD study in RA patients. As a precaution, the IV infusion of mavrilimumab in our study will be administered at slower rates than those applied in the SAD study.

5. Study population

The study population includes adult male and female patients who are hospitalized and diagnosed with severe COVID-19-induced pneumonia and hyperinflammation.

5.1 Inclusion criteria

Participants eligible for inclusion in this protocol must meet all of the following criteria:

- 1. Adults (≥ 18 years of age)
- 2. Signed informed consent by any patient capable of giving consent, or, when the patient is not capable of giving consent, by his or her legal/authorized representative or according to local guidelines
- 3. Patients clinically diagnosed with SARS-CoV-2 virus by PCR or by other approved diagnostic methodology
- 4. Hospitalized with COVID-19-induced pneumonia evidenced by chest x-ray or CT scan with pulmonary infiltrates
- 5. Patient requiring oxygen supplementation (i.e. with a SpO2 \leq 92% while breathing room air) and having a PAO₂/FIO₂ ratio \leq 300 mmHg
- 6. Lactate dehydrogenase (LDH) > normal range and at least one of the following:
 - fever > 38.0 °C;
 - increased levels of C-reactive Protein (CRP) $\geq 10x$ UNL mg/L (≥ 60 mg/l);
 - increased levels of ferritin $\geq 2.5 \times UNL$ ($\geq 1000 \, \mu g/L$)

5.2 Exclusion criteria

Participants meeting **any** of the following criteria are not eligible for inclusion in this protocol:

- Onset of COVID-19 pneumonia symptoms (i.e. dyspnea/respiratory insufficiency) >14 days
- 2. On mechanical ventilation at the time of randomization
- 3. A $PaO_2/FiO_2 < 100 \text{ mmHg}$

- 4. Uncontrolled systemic infection (other than COVID-19)
- 5. Hypersensitivity to the active substance or to any of the excipients of the experimental drug
- 6. Total neutrophil count < 1500/mm³
- 7. Severe hepatic cirrhosis
- 8. History of chronic HBV or HCV infection
- 9. Known or active tuberculosis (TB) or a history of incompletely treated TB; suspected or know extrapulmonary tuberculosis
- 10. Moderate/severe heart failure (NYHA Class 3 or 4)
- 11. Any prior (within the defined periods below) or concurrent use of immunosuppressive therapies including but not limited to the following:
 - a. Anti-IL-6, anti-IL-6R antagonists or Janus kinase inhibitors (JAKi) in the past 30 days or plans to receive during the study period;
 - b. Cell-depleting agents (e.g., anti CD20) without evidence of recovery of B cells to baseline level;
 - c. Anakinra within 1 week of baseline; canakinumab within 8 weeks of baseline; abatacept within 8 weeks of baseline.
 - d. Tumor necrosis factor (TNF) inhibitors within 2-8 weeks (etanercept within 2 weeks, infliximab, certolizumab, golimumab, or adalimumab within 8 weeks), or after at least 5 half-lives have elapsed, whichever is longer;
 - e. Alkylating agents including cyclophosphamide (CYC) within 6 months of baseline;
 - f. Cyclosporine (CsA), azathioprine (AZA) or mycophenolate mofetil (MMF) or leflunomide or methotrexate within 4 weeks of baseline.
- 12. Pregnancy or lactation (Note: Women of childbearing age should use effective contraception/abstinence after treatment with mavrilimumab and for 3 months after the dosing)
- 13. Any serious medical condition or abnormality of clinical laboratory tests that, in the investigator's judgment, precludes the patient's safe participation in and completion of the study
- 14. In the opinion of the investigator, progression to death is imminent and highly likely within the next 24 hours, irrespective of the provision of treatments
- 15. Current participation in any other interventional investigational trials

6. Treatment plan

The study will enroll patients who require hospitalization with supportive care for COVID-19 pneumonia, including supplemental oxygen. All patients will receive, in addition to the best available standard of care, mavrilimumab or placebo. One single dose of mavrilimumab or placebo will be given.

6.1 Investigational drug

Mavrilimumab

Mavrilimumab (KPL-301) 6 mg/kg of body weight. The drug product is a sterile solution formulated in 50 mM sodium acetate, 70 mM NaCl, 4% (w/v) trehalose dihydrate, 0.05% (w/v) polysorbate-80, pH 5.8. Mavrilimumab will be diluted to a final concentration of 50 mg/mL, so 0.12 mL/kg of the final dilution will be administered on day 1 over approximately 1 hr with a syringe pump.

Diluent/Placebo

A matching dose (0.12 ml/kg of body weight) of placebo (a sterile solution formulated in 50 mM sodium acetate, 70 mM NaCl, 4% (w/v) trehalose dihydrate, 0.05% (w/v) polysorbate-80, pH 5.8) will be administered on day 1 over approximately 1 hr with a syringe pump.

Mavrilimumab or diluent/placebo will be prepared by the unblinded pharmacist. Details on the requirements for storage and management of study treatment, and instructions to be followed for participant numbering, prescribing/dispensing, and taking study treatment are outlined in the pharmacy manual.

All infusions should be administered in the presence of qualified health care personnel as per local hospital regulations under the supervision of the investigator or designee. Immediate access to an emergency crash cart is required. The infusion should last approximately one hour. Premedication to avoid or treat potential infusion-related reaction is at the discretion of the investigator. It is recommended that in the initial 15 minutes the rate of administration

should allow for delivery of approximately 1/6 of the total volume of the infusion. If no moderate or severe infusion reactions are observed by the Investigator, the rate can be doubled for the next 15 minutes. Adjudication of infusion reaction severity is at the discretion of the investigator. After the first 30 minutes the rate can be increased with another 50% if infusion continues to be well tolerated. An example of infusion rates for this protocol would be: 1ml/min in first 15 minutes, followed by 2ml/min during 16-30min, and 3ml/min for the remaining 30 minutes. At any time during the drug administration, if a moderate reaction occurs, the infusion should be stopped and restarted at the discretion of the investigator only after the events have resolve. The infusion should be stopped permanently if a severe reaction is observed.

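### The example infusion rates in Section 6.1 add up to 135 mL, but the dose is 0.12 mL/kg; at those rates anyone up to 125 kg gets the whole dose in the first 15 minutes instead of about an hour.

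*Protocol*

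**What the plan says.** Section 6.1 gives the dose as "Mavrilimumab (KPL-301) 6 mg/kg of body weight" and derives the volume from the concentration: "Mavrilimumab will be diluted to a final concentration of 50 mg/mL, so 0.12 mL/kg of the final dilution will be administered on day 1". Delivery is by syringe pump over about an hour, and the section repeats the duration on its own: "The infusion should last approximately one hour". Placebo has the same volume per kilogram. Section 4 repeats both the 50 mg/mL and the one-hour duration, including for placebo: "Patients in the placebo arm will be treated with an equal amount of placebo infused IV over approximately 1 hour".

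Section 6.1 also recommends a graded start. The rate in the first 15 minutes "should allow for delivery of approximately 1/6 of the total volume of the infusion". Then: "If no moderate or severe infusion reactions are observed by the Investigator, the rate can be doubled for the next 15 minutes". After 30 minutes the rate may rise by a further 50% if the infusion is still tolerated.

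The section then gives the only absolute pump rates in the protocol, as an example: "1ml/min in first 15 minutes, followed by 2ml/min during 16-30min, and 3ml/min for the remaining 30 minutes".

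**The concern.** The example cannot be reconciled with the volume and duration in the same section. Its rates suit an infusion of well over 100 mL, whereas the protocol specifies a syringe holding roughly 6 to 14 mL for patients of 50 to 120 kg (assumed weights; the protocol gives none).

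What is at stake is infusion safety. Section 6.1 makes each rate increase conditional on tolerance, so that only a small share of the antibody has gone in before the first check. Section 4.2 says that, as a precaution, the infusion here will run more slowly than in the earlier single-ascending-dose study. Section 10.1 lists hypersensitivity among the events of special interest, and the participants are hypoxaemic on entry. A nurse or pharmacist who took the printed mL/min figures at face value would defeat that graded start.

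**Working it through.** **Inputs.** From Section 6.1: dose 6 mg/kg; final concentration 50 mg/mL; duration about 60 min; about 1/6 of the volume in the first 15 min, then rate ×2, then rate ×1.5; example rates 1, 2 and 3 mL/min for 15, 15 and 30 min. Body weight is not given, so 50 to 150 kg is assumed for illustration.

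**1. The protocol's own volume.** 6 mg/kg ÷ 50 mg/mL = 0.12 mL/kg. This agrees with the text.

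**2. Volume implied by the example.** 1×15 + 2×15 + 3×30 = 15 + 30 + 90 = 135 mL. Matching weight: 135 ÷ 0.12 = 1125 kg. For 135 mL to hold the 420 mg dose of a 70 kg patient, the solution would have to be 420 ÷ 135 = 3.1 mg/mL, not 50 mg/mL.

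**3. Weight at which the first step holds the whole dose.** The first step delivers 15 mL; 15 ÷ 0.12 = 125 kg. This threshold needs no assumption about weight.

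**4. Time to give the full dose at the example rates.** With V = 0.12 × weight, the time is V minutes if V ≤ 15 mL, otherwise 15 + (V − 15)/2 minutes.

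| Assumed weight (kg) | Volume (mL) | Time at example rates (min) | Mean rate for 60 min (mL/min) |
|---|---|---|---|
| 50 | 6.0 | 6.0 | 0.10 |
| 70 | 8.4 | 8.4 | 0.14 |
| 80 | 9.6 | 9.6 | 0.16 |
| 120 | 14.4 | 14.4 | 0.24 |
| 125 | 15.0 | 15.0 | 0.25 |
| 150 | 18.0 | 16.5 | 0.30 |

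The 1 mL/min start is 1 ÷ 0.14 = 7.1 times the mean rate needed at 70 kg, and 1 ÷ 0.24 = 4.2 times at 120 kg. Compared with the starting rate under the 1/6 rule at 70 kg (8.4 ÷ 6 ÷ 15 = 0.093 mL/min), it is 10.7 times too fast.

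**5. Is the written rule itself sound?** With both increases, the shares are 1/6 in 15 min, 2/6 in the next 15 min, and the remaining 3/6 at a rate of 3/6 per 15 min: 45 min in total. With the doubling only, the last half takes 22.5 min: 52.5 min. With no increase: 6 × 15 = 90 min. The range of 45 to 90 min fits an infusion of about one hour, so the mL/min example is the one outlier. Even on its own terms the example starts with 15 ÷ 135 = 1/9 of its volume, not 1/6.

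**6. Rates that would fit.** Keeping the 1:2:3 pattern over 60 min, the starting rate is V ÷ 135. At 70 kg this gives 0.062, 0.124 and 0.187 mL/min. Check: 15×0.0622 + 15×0.1244 + 30×0.1867 = 0.93 + 1.87 + 5.60 = 8.4 mL.

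**The case against.** The strongest reply is that nobody would follow the example literally. It is labelled an example, and the surrounding step-up scheme is worded as a recommendation. The one-hour duration is stated repeatedly in Section 6.1, in Section 4 and in the synopsis. The example's own timetable runs to 60 minutes, so a syringe that empties in 8 minutes would show at once that something is wrong. The pharmacy manual is not shown and may give workable rates. Section 6.1 also requires qualified staff, immediate access to a crash cart, and stopping for a moderate or severe reaction at any time.

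It can also be said that the check at 15 minutes governs a rate increase, and no increase occurs if the syringe is already empty.

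Much of this stands as a limit on the consequence. Monitoring for reactions does not disappear, and the documents give neither the infusion rate of the earlier study nor reaction rates by speed, so the added clinical risk cannot be sized. None of it makes the figures right. They are the only pump settings the protocol prints, and they are presented as applying to this trial. The purpose of the check is to look for a reaction while about five sixths of the dose is still in the syringe; under the example, nothing is left up to 125 kg.

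**Conclusion.** The point holds. The example rates contradict the volume and duration fixed in the same section, and nothing elsewhere in the protocol resolves the conflict. Followed as printed, they deliver the full dose in 6.0 to 14.4 minutes for assumed weights of 50 to 120 kg, roughly 4 to 10 times faster than the intended hour. The 135 mL total and the 125 kg threshold rest only on the protocol's own numbers; the individual times depend on the assumed weights.

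This is an error of infusion rate, not of dose: the patient still receives 6 mg/kg. Both arms have the same volume, so blinding is untouched, and neither sample size nor analysis is affected. It should be fixed because it sits in an operative dosing section and bears on participant safety.

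**What to change.** Delete the mL/min example from Section 6.1. Deletion alone is enough, because the 1/6 rule with its optional increases already gives an infusion of about an hour.

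If sites need pump settings, replace the example with weight-based rates that deliver 0.12 mL/kg in about 60 minutes. If the 1:2:3 pattern is kept, that means 1/9, 2/9 and 6/9 of the volume over 15, 15 and 30 minutes (at 70 kg about 0.06, 0.12 and 0.19 mL/min). The recommended starting fraction should then agree with the pattern chosen, since 1:2:3 over 60 minutes starts with 1/9 rather than 1/6.

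In either case, check that the pharmacy manual gives the same rates. The cost is one sentence, possibly the starting fraction beside it, and that check. Dose, volume, blinding and analysis do not change.

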6.2 Concomitant treatments

All medications, procedures, and significant non-drug therapies (including but not limited to pronation, physical therapy, and blood transfusions) administered after the participant was enrolled into the study must be recorded on the appropriate CRF.

Each concomitant drug must be individually assessed against all exclusion criteria/prohibited medication. If in doubt, the investigator should contact the Promoter before randomizing a participant or allowing a new medication to be started. If the participant is already enrolled, contact the Promoter to determine if the participant should continue participation in the study.

The patient must be told to notify the Treating Physician about any new medications that he/she takes after the start of mavrilimumab, also after potential discharge from the hospital.

6.3 Permitted concomitant therapy requiring caution and/or action

Patients in this study will be enrolled to mavrilimumab or placebo/diluent, in addition to standard of care per local practice, which may include anti-viral treatment, antimalarials,

corticosteroids (≤ 15 mg of prednisone or equivalent) and supportive care. Immunomodulator (topical or inhaled) use for asthma and atopic dermatitis are not restricted. Use of oral, injected or implanted hormonal methods of contraception are allowed while on mavrilimumab.

In worsening patients, treatment with investigational COVID-19 treatments, such as but not limited to antimicrobials, interferon beta, or convalescent serum, is permitted, if approved by the Promoter. Particular attention should be taken when considering rescue treatment with biologic or targeted-synthetic DMARDs/immuno-suppressors due to the risk of potential severe immune-suppression if given in combination with the investigational drug. Systemic corticosteroids (low- or high-dose per medical judgement) could also be used as a rescue medication.

Information that should be gathered and recorded on the CRF on these medications include:

- · Reason for use
- Dates of administration including start and end dates
- Dosage information including dose and frequency

